8.1.3. Incurred sample reproducibility

In order to establish the reproducibility of the assay with incurred samples, at least 10% of the total analyzable study samples will be selected and re-assayed. The replicate measurement is not to be averaged with the original one, but both values will be presented in the bioanalytical report with the initial value being used for PK calculations. The concentrations of the original and replicate samples will be tabulated, along with the percent difference between the two values.

8.2. SAFETY DATA

The safety population will include all subjects who received at least one treatment under study.

Descriptive statistics will be used to summarize adverse events, safety results and demographic variables (age, height, weight and BMI).

The laboratory tests and the measurements of vital signs, visual skin evaluation and other safety parameters performed after treatment are mainly performed for safety reasons, and changes may occur without any clinical symptoms. Therefore, any significant changes will be recorded as adverse events only if they are judged clinically significant by the Medical Investigator.

The laboratory tests will be carried out according to the standard operating procedures of the licensed medical laboratory. Abnormal results will be verified to rule out laboratory error. Persistent relevant abnormal values should be followed up until the cause is determined or until the values return to the pre-medication value.

9. PHARMACOKINETICS AND STATISTICS

9.1. SUBJECTS TO ANALYZE

Samples from all subjects who received at least one treatment and for whom sufficient number of blood samples was taken for pharmacokinetic analysis will be assayed and included in the pharmacokinetic analysis.

Subjects who do not complete the sampling schedule of one or more study periods may be included in the pharmacokinetic analysis for only the PK parameters that are judged not to be affected by the missing sample(s). This decision is to be documented by the SRA department and approved by the sponsor before the start of the sample analysis by the bioanalytical facility.

9.2. PHARMACOKINETIC ANALYSIS

No or negligible plasma levels of chlorhexidine are expected following a single topical application of ReadyPrep[®] CHG. Chlorhexidine plasma concentrations produced by each treatment will be determined in order to establish the pharmacokinetic profile of the drug product. Below limit of quantitation concentrations (coded BLQ) will be treated as zero for all statistical analyses. In the event that chlorhexidine levels are measurable, the pharmacokinetic parameters that will be derived from the plasma concentrations (see Section 6.2.1) will be taken into consideration for evaluation of PK parameters.

In the case where concentrations of chlorhexidine cannot be determined due to bioanalytical or clinical reasons, these values will be set to missing for the pharmacokinetic analysis.

In the case where less than 3 consecutive measurable concentrations of chlorhexidine are observed, the AUC parameters will not be estimated for that specific study period.

In order to better understand and control for the presence of chlorhexidine in the environment, baseline levels will be assessed in each study period. The pharmacokinetic parameters for chlorhexidine will be presented both adjusted for baseline and unadjusted. The baseline adjustment will consist of the following:

- Baseline concentrations will be measured approximately 10.00, 2.00 and 0.50 hours prior to each treatment. The mean of these 3 pre-dose concentrations will be used for baseline adjustment.
- Concentrations post-dose will be adjusted for each subject during each period by subtracting the mean baseline value corresponding to that subject. Baseline adjustment will therefore be subject- and period- specific.

If subtraction leads to values of adjusted profile that would be below the LOQ, these values will be reported without any change and they will not be reported as BLQ. However, if a negative plasma concentration value results after baseline adjustment, this value will be set to 0 prior to calculating the baseline-adjusted AUC.

For baseline adjusted calculations, concentrations at time T= -0.50 h will be set to zero given that no concentration provided by the given treatment is expected to be present at this time point. Unadjusted baseline PK estimation will use the observed concentration value at time T=-0.50 h.

The main pharmacokinetic parameters of interest for this study will be C_{max} , AUC_{0-T} and $AUC_{0-\infty}$. Other parameters such as T_{max} , $AUC_{0-T/\infty}$, λ_Z and T_{half} will be provided for information purposes only.

The main absorption and disposition parameters will be estimated using a non-compartmental approach with a log-linear terminal phase assumption. The trapezoidal rule will be used to estimate the area under the curve (linear trapezoidal linear interpolation) and the terminal phase will be estimated by maximizing the coefficient of determination estimated from the log-linear regression model. However, $AUC_{0-\infty}$, $AUC_{0-T/\infty}$, λ_Z and T_{half} parameters will be estimated for individual concentration-time profiles only when the terminal log-linear phase can be reliably characterized using the following criteria:

- Phoenix[®] WinNonlin[®] Best fit range selection
- R^2 of at least 80%
- The corresponding terminal half-life value must be lower than or equal to 2 times the time interval over which λ_Z was estimated (i.e. $T_{half} \leq$ twice the time interval difference between T_{LQC} and T_{LIN}).

Descriptive statistics will be calculated for plasma concentrations at each individual time point and for all pharmacokinetic parameters. The individual plasma concentration/time profiles will be presented using the actual sampling times whereas the mean plasma concentration/time profiles will be presented using the theoretical sampling times.

Pharmacokinetic analyses will be generated using validated pharmacokinetic software (i.e. Phoenix[®] WinNonlin[®] version 6.3 or higher, Phoenix[®] ConnectTM version 1.3.1 or higher).

9.3. STATISTICAL ANALYSIS

No statistical analysis will be performed.

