1. INTRODUCTION

Chlorhexidine [CHD; 1,1'-hexamethylenebis[5-(4-chlorophenyl) biguanide]] has a wide spectrum of bactericidal and antiviral activity and is a common ingredient in various formulations ranging from skin disinfectants in healthcare products to antiplaque agents in dentistry. The presence of two symmetrically positioned basic chlorophenyl guanide groups attached to a lipophilic hexamethylene chain aid in rapid absorption through the outer bacterial cell wall, causing irreversible bacterial membrane injury, cytoplasmic leakage, and enzyme inhibition. Chlorhexidine exists as various forms of salts: diacetate, dihydrochloride, or digluconate, mainly differing by their solubilizing abilities in aqueous or oily media. Chlorhexidine digluconate (or gluconate), as most soluble in water or alcohol, is the most used form in topical dermatology or cosmetic preparations.^{1,2}

As chlorhexidine is not significantly absorbed through intact skin³ no systemic adverse events are expected. However, skin reaction could occur.

ReadyPrep[®] CHG is composed of 2% chlorhexidine gluconate (CHG) solution on a single fiber, polyester cloth. Each cloth contains 500 mg CHG. The sponsor is developing ReadyPrep[®] CHG (2% Chlorhexidine Gluconate Cloth) for patient preoperative skin preparation.

In order to better understand and control for the presence of chlorhexidine in the environment, baseline levels will be assessed in each study period and a control treatment arm will be included.

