2. STUDY OBJECTIVES

The primary objective of this study is to demonstrate that no or negligible systemic exposure occurs after a single topical application of ReadyPrep[®] CHG.

The secondary objective of this study is to determine the safety and tolerability of a single topical application of ReadyPrep[®] CHG in healthy volunteers after a single topical application.

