6.1.2.1. Drug administration procedure

ReadyPrep[®] CHG Application (Treatment-1 and Treatment-2):

In two Treatment-1 and -2, a single topical application of ReadyPrep[®] CHG will be done on either the abdomen (surface area of approximately 5 x 5 inches) or the groin (surface area of approximately 5 x 2 inches) according to the randomization scheme.

The drug will be applied to a clean, dry, non-irritated, normal skin area. Possible hairs will be removed by means of scissors (no shaving) on the morning of dosing.

Approximately 30 minutes prior to any application, the site should be gently washed with room temperature water and dried without rubbing or heavy pressure with a gauze or similar cotton soft material. The application site must be allowed to dry for at least 15 minutes before drug application. After drying, the application site will be marked for dose location.

The topical application of ReadyPrep[®] CHG will consist of a 3-minute vigorous rub followed by a 1 minute dry time at the application site. The

1-minute dry time will be air drying without dabbing or rubbing. The time of dosing will be defined as the start time of the drug application on the skin.

Control Treatment (Treatment-3):

In Treatment-3, the same procedures as Treatment-1 and -2 will be performed, but without the topical application of ReadyPrep® CHG or placebo (no placebo ReadyPrep[®] cloth will be provided or used). Therefore, approximately 30 minutes prior, the site should be gently washed with room temperature water and dried without rubbing or heavy pressure with a gauze or similar cotton soft material. The application site must be allowed to dry for at least 15 minutes and after drying, the skin site will be marked. Subjects should be placed in the same position, for the same length of time, in the same area as they would be dosed.

The physician will remain at the clinical site for at least the first 4 hours following each treatment and will remain available at all times during the entire period of the study.

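### The primary objective is to demonstrate no or negligible exposure, but the protocol limits itself to descriptive summaries, sets no limit for negligible and defines no contrast with the control period

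*Protocol*

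**What the plan says.** Protocol section 2 states: "The primary objective of this study is to demonstrate that no or negligible systemic exposure occurs after a single topical application". The synopsis has the same objective. Section 9.4 repeats it and judges 12 subjects sufficient on the basis of sponsor data that it does not show.

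Section 9.3, and the Statistics entry of the synopsis, state: "No statistical analysis will be performed". Sections 8.2 and 9.2 do plan descriptive statistics for safety data, for concentrations at each time point and for all pharmacokinetic parameters.

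The word negligible recurs in section 9.2 as an expectation only: "No or negligible plasma levels of chlorhexidine are expected following a single topical application of" the product. No concentration, AUC, count of subjects or decision rule is attached to it.

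On environmental chlorhexidine, the Introduction says that "baseline levels will be assessed in each study period and a control treatment arm will be included". Appendix 1 gives control of environmental chlorhexidine as a reason for Amendment 01, which added the control treatment. Section 9.2 then defines one correction: "The mean of these 3 pre-dose concentrations will be used for baseline adjustment", and "Baseline adjustment will therefore be subject- and period- specific". It defines no difference or ratio of Treatment-1 or Treatment-2 against Treatment-3.

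**The concern.** An objective to demonstrate something needs a statement of which result would meet it and which would not. Here there is none, and the protocol rules out the analysis that could supply one. This is a stated choice: an analysis plan that added such an analysis would contradict section 9.3.

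The control period makes the gap practical. It was added because background chlorhexidine was thought possible. If background is measurable, the within-period correction can produce apparent exposure where nothing was absorbed. Whether the treated periods exceed the control period, and whether any excess is negligible, would then be settled after the data are seen.

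**Working it through.** **1. The plan's own figure.** The 12 subjects of section 9.4 cannot be reproduced. The protocol gives no margin, variability, error rate, power, expected proportion quantifiable or drop-out rate.

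**2. Adjusted Cmax with no absorption.** From Table 2 there are 9 post-dose and 3 pre-dose samples per period. The documents give no quantification limit, background level or variability, so the following is assumed: flat background, normal noise with total SD sigma, and a share rho of the variance common to all samples of a profile. The common part cancels on subtraction and leaves noise of SD sigma × √(1 − rho). The expected maximum of 9 independent standard normal values is 1.485, and the mean of 3 has expectation 0. So:

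E(adjusted Cmax) = 1.485 × √(1 − rho) × sigma

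| rho | Mean, in sigma | As % of background at CV 30% |
|---|---|---|
| 0 | +1.48 | 45% |
| 0.5 | +1.05 | 32% |
| 0.9 | +0.47 | 14% |

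The chance that it is positive is about 97% in each row, because the scale cancels. With values below the limit of quantification set to 0, as section 9.2 requires, simulation gives these proportions of periods with a positive value:

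| Samples quantifiable | rho 0 | rho 0.5 | rho 0.9 |
|---|---|---|---|
| 10% | 61% | 38% | 20% |
| 2% | 17% | 11% | 5% |

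If no sample is quantifiable, the effect is absent.

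**3. What the control period offers.** With no absorption the same bias is present in Treatment-3, so the paired difference in adjusted Cmax averages 0. The SD of adjusted Cmax is 0.832 × √(1 − rho) sigma. With 12 pairs the 90% interval half-width is t(0.95; 11) × 0.832 × √(1 − rho) × √(2/12) = 0.61, 0.43 or 0.19 sigma for rho = 0, 0.5 or 0.9.

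**4. Where that difference fails.** Under real absorption it shrinks toward zero. Assume a true peak of 1 sigma and all samples quantifiable. For a one-compartment curve (absorption rate 1/h, elimination rate 0.2/h), the expected paired difference is 0.68, 0.71 or 0.78 sigma. For a rise at a single sample it is 0.22, 0.28 or 0.54 sigma.

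Now set a limit that the one-sided 95% upper confidence limit would fall below with 80% probability if there were no difference: 0.90, 0.64 or 0.29 sigma. If the true peak equals that limit, the upper confidence limit still falls below it in about 20–21% of trials (curve) or 61–62% (single sample), against a nominal 5%.

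**5. Paired AUC.** Section 9.2 says: "In the case where less than 3 consecutive measurable concentrations of chlorhexidine are observed, the AUC parameters will not be estimated". With 10% of samples quantifiable, about 1% to 10% of no-absorption profiles have three consecutive measurable values. Among 12 control periods that is about 12 × 0.009 = 0.1 to 12 × 0.096 = 1.2 AUCs. A subject who absorbs drug over a clean background has a treated AUC and no control AUC, so the pair is lost.

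**6. Counts.** If no subject has a quantifiable post-dose value, the exact one-sided 95% upper limit for the true proportion is 1 − 0.05^(1/12) = 22%. Section 5.1 does not replace drop-outs. With two lost it is 1 − 0.05^(1/10) = 26%.

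**The case against.** The best defence is that a 12-subject Phase I pharmacokinetic study may properly be descriptive. Section 9.3 should be read with sections 8.2 and 9.2, so what it excludes is inference. This stands. A reader might infer that no analysis at all is planned, or that the control data go unused. The documents do not support either: the control period gets the same parameters and summaries, so a bias common to all periods could be seen informally. What remains is that a descriptive plan does not match the word demonstrate, or the claim in section 9.4 that 12 subjects suffice for it.

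A second defence is that the bias in adjusted Cmax runs against the sponsor, that unadjusted parameters are also presented, and that section 9.2 expects little or no measurable drug. This also stands. A reader might infer that the bias could produce a false finding of negligible exposure, but its direction is upward. Even so, the protocol does not write down that all samples below the limit of quantification would meet the objective, and it does provide for measurable levels.

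A third defence is that limits and contrasts are often left to an analysis plan. Taken alone they would be. Here section 9.3 closes that route.

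**Conclusion.** The mismatch holds and should be corrected. The objective claims a demonstration, the plan allows only description, no limit for negligible exists, and the control period has no defined contrast with the treated periods. The data would remain usable; what is lost is a conclusion fixed in advance.

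The size of the adjusted-Cmax effect, about +0.5 to +1.5 sigma and positive in about 97% of periods, rests on assumed normal noise around a flat, fully quantifiable background. It falls as fewer samples are quantifiable. The upward direction when background is measurable follows from comparing a maximum with a mean.

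Two stronger readings should be resisted. One is that 12 subjects are too few: with no margin or variability given, the documents support neither that nor sufficiency. The other is that comparing the upper confidence limit of the paired Cmax difference with a limit would repair the plan. Step 4 shows that this rule would declare exposure negligible too often.

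**What to change.** 1. Reword the objective in the synopsis and section 2, and the claim in section 9.4, as descriptive, for example: to estimate systemic exposure.
2. In section 9.3 and the synopsis, replace the exclusion of statistical analysis with within-subject descriptive comparisons. Lead with the number of subjects with any quantifiable post-dose value, by treatment, with exact confidence limits. If levels are measurable, add paired Treatment-1 minus Treatment-3 and Treatment-2 minus Treatment-3 differences with confidence intervals, for baseline-adjusted Cmax and for the concentration at each time point. State that the Cmax difference is unbiased only under no absorption and is attenuated toward zero when absorption is real.
3. Do not use the upper confidence limit of the paired Cmax difference as a test of negligible exposure. Do not rely on paired AUC0-T where the control AUC is not estimable. An interval that covers 0 does not by itself show negligible exposure, and the 22% limit describes only the chance of any quantifiable value.
4. If the sponsor keeps the word demonstrate, it must fix a limit before samples are assayed and apply it to a measure that is not attenuated by taking a maximum.

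The cost is wording, a little more analysis and a more qualified conclusion. No subjects, samples or visits are added.

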9.4. SAMPLE SIZE JUSTIFICATION

The objective of this study is to demonstrate that no or negligible systemic exposure occurs after a single topical application of ReadyPrep[®] CHG. Based on the sponsor's data, it is estimated that 12 subjects should be sufficient to meet this objective.

10.REGULATORY REQUIREMENTS

10.1. LIABILITIES

It is the sponsor's responsibility to guarantee sufficient insurance coverage should any serious events or deaths result directly or not from the execution of the present protocol.

The present article is not to be interpreted as engaging the sponsor's responsibility in the event of fault or negligence of the subjects, investigators, or any persons or employees under the control of the clinical site.

10.2. STATEMENT OF INVESTIGATOR

The FDA 1572 form, Statement of Investigator [Title 21, CFR Part 312], will be signed by the Principal Investigator, and will be kept on file and will remain available upon request.

10.3. DELEGATION OF INVESTIGATOR DUTIES

The Principal Investigator will ensure all personnel involved in the trial are adequately qualified and informed about the protocol, any amendments to the protocol, the study treatments, and their trial-related duties and functions.

The Principal Investigator will maintain a list of sub-investigator(s) and other appropriately-qualified persons to whom he delegates significant trial-related duties.

Should the Principal Investigator delegate the supervision of the investigational product administration to a designated person, this individual must have the appropriate medical legal qualifications. The Principal Investigator should also ensure key staff personnel have the appropriate medical qualifications to effectively conduct or supervise any potential resuscitation procedures.

10.4. INSTITUTIONAL REVIEW BOARD (IRB)

This protocol and the ICF will be submitted to an IRB (or IEC) prior to initiation of the study and the study will not start until the Board has approved the documents. Notification of the Board's approval will be appended to the final report.

This study will be conducted in compliance with the study protocol, the ethical principles that have their origins in the Declaration of Helsinki, the ICH Guideline E6

for GCP, the FDA GCP Code of Federal Regulations (CFR) Title 21 (part 56), and the European regulation EU 536/2014.

10.5. INFORMED CONSENT FORM (ICF)

Before screening activities can commence, each volunteer will be given a copy of the consent to read, and a full explanation of the purpose of the study, the procedures to be carried out, and the potential adverse event(s). Once this essential information is provided to the volunteer and the medical investigator or designee has the conviction the volunteer understands the implications of participating in the study, if the volunteer(s) chooses to continue screening, they will be requested to sign and date a properly executed written informed consent document in compliance with the U.S. Code of Federal Regulations (Title 21, Part 50). Subjects will be assured they may withdraw from the study at any time without jeopardizing their medical care or future study participation (for which they qualify). They will be given a signed copy of the informed consent.

If an amended or revised ICF is introduced during the study, each subject's further consent should be obtained.

10.6. CASE REPORT FORM

Data required by the protocol will be accurately reported on the CRF for each subject included (i.e., who received an Investigational Product treatment) in a clinical trial. The complete CRF will be approved and signed by the Principal Investigator or designee, who will receive a signature delegation from the investigator.

A copy of the CRFs will be provided to the sponsor with the final report.

10.7. RECORD RETENTION

All essential documents and records will be maintained by the clinical site in accordance with, and for the period specified in the applicable regulatory requirement(s) (FDA CFR 312.57 (C)).

10.8. QUALITY ASSURANCE/QUALITY CONTROL

Designated personnel from Algorithme Pharma will be responsible for maintaining quality assurance (QA) and quality control (QC) systems to ensure that the trial is conducted and data are generated, documented and reported in compliance with the protocol, ICH Guideline E6 for Good Clinical Practices, applicable requirements as outlined in the FDA and OECD Principles of GLP, and the *Reflection paper for*

laboratories that perform the analysis or evaluation of clinical trial samples (EMA/INS/GCP/532137/2010).

10.9. MONITORING OF THE STUDY

The sponsor or its representative may visit the study facilities at any time in order to maintain current and personal knowledge of the study through review of the records, comparison with source documents, observation and discussion of the conduct and progress of the study. The clinical site will permit trial-related monitoring, audits, IRB/IEC review, and regulatory inspection(s) by providing direct access to source data/documents.

